3.2 DISCUSSION OF TRIAL DESIGN, INCLUDING THE CHOICE OF CONTROL GROUP(S)

This is an approximately 8 weeks Phase I trial in healthy volunteers consisting of the two treatment parts.

The design of this clinical photosensitivity study followed the general concepts of ICH S10 (a recently published international guideline on "Photosafety Evaluation of Pharmaceuticals"), and included ciprofloxacin as a positive control (R19-2247).

Three distinct exposure conditions were included to account for seasonal and regional differences in human exposure to sunlight.

A two-layer randomization process will be employed:

Allocation to the Study part: Subjects will be randomly allocated to part A or part B in a 3:1 ratio in an open-label manner. Randomization numbers defining subject allocation to study part will be assigned in ascending, sequential order to eligible subjects.

Treatment Part A will be conducted according to a randomized, double blind, placebo-controlled design.

It is standard in trials involving healthy volunteers to include a placebo group as control for the evaluation of safety. Treatment Part A group will consist of 36 subjects in 400 mg QD group and 36 subjects in 300 mg BID group, with each group having 27 on active treatment and 9 on placebo.

The treatment will be blinded throughout the whole trial, to minimize any bias that could be introduced by knowledge of the treatment by either the investigator or the subject.

[figure not shown]
Treatment Part B will be conducted according to an open-label, observer-blinded design to assess the photosensitivity potential of ciprofloxacin (a mild photosensitizer) as a positive control.

c27983101-03 Clinical Trial Protocol Page 33 of 79

Proprietary confidential information © 2020 Boehringer Ingelheim International GmbH or one or more of its affiliated companies

12 subjects will receive 500 mg ciprofloxacin b.i.d. over 5 days with a single dose on the 6^{th} day.

The open-label treatment is not expected to bias the photosafety results, since the trial endpoints derived from the photosensitivity assessments will be provided by an observer performing skin evaluations which is blinded to treatment allocation.

3.3 SELECTION OF TRIAL POPULATION

It is planned that in total up to 84 healthy male and female subjects will enter the trial. Subjects who prematurely discontinue the trial due to any reason may be replaced to ensure sufficient number complete the trial. Thus the planned number of subjects entered may exceed a total of 84. They will be recruited from the volunteers' pool of the trial site.

A log of all subjects enrolled into the trial (i.e. who have signed informed consent) will be maintained in the Investigator Site File (ISF) irrespective of whether they have been treated with investigational drug or not.

If a subjects is enrolled in error (does not meet all inclusion criteria or meets one or more exclusion criteria on the day of enrolment), the sponsor should be contacted immediately.

c27983101-03 Clinical Trial Protocol Page 34 of 79

Proprietary confidential information © 2020 Boehringer Ingelheim International GmbH or one or more of its affiliated companies

3.3.1 Main diagnosis for trial entry

The trial will be performed in healthy male and female subjects.

Please refer to section 8.3.1 (Source Documents) for the documentation requirements pertaining to the in- and exclusion criteria.

3.3.2 Inclusion criteria

- 1. Healthy male and female subjects according to the assessment of the Investigator, based on a complete medical history, physical examination (including dermatological skin type assessment), vital signs (blood pressure, pulse rate), 12-lead ECG, and clinical laboratory tests
- 2. 18 to 55 years old
- 3. BMI 18 to 35 kg/m (incl.)
- 4. Fitzpatrick skin type I, II, or III:
 - I Always burns easily, never tans
 - II Always burns easily, tans minimally
 - III Burns moderately, tans gradually
- 5. No ultraviolet exposure of the test areas 4 weeks prior to baseline photo testing
- 6. Normal skin response during preliminary photo testing.
- 7. Signed and dated written informed consent in accordance with ICH-GCP and local legislation prior to admission to the trial.
- 8. Women of childbearing potential (WOCBP)¹ must be ready and able to use highly effective methods of birth control per ICH M3 (R2) that result in a low failure rate of less than 1% per year when used consistently and correctly. A list of contraception methods meeting these criteria is provided in the patient information

Permanent sterilisation methods include hysterectomy, bilateral salpingectomy and bilateral oophorectomy.

Tubal ligation is NOT a method of permanent sterilisation.

Tuodi figation is NOT a method of permanent stermsation.

A postmenopausal state is defined as no menses for 12 months without an alternative medical cause.

¹ A woman is considered of childbearing potential (WOCBP), i.e. fertile, following menarche and until becoming postmenopausal unless permanently sterile.

Boehringer Ingelheim

BI Trial No.: 1407-0037

c27983101-03 Clinical Trial Protocol Page 35 of 79

Proprietary confidential information © 2020 Boehringer Ingelheim International GmbH or one or more of its affiliated companies

3.3.3 Exclusion criteria

- 1. Any finding in the medical examination (including blood pressure, pulse rate or ECG) deviating from normal and judged as clinically relevant by the Investigator.
- 2. Any laboratory value outside the reference range that the Investigator considers to be of clinical relevance.
- 3. Gastrointestinal, hepatic, renal, respiratory, cardiovascular, metabolic, immunological or hormonal disorders or any evidence of a concomitant disease judged as clinically relevant by the Investigator.
- 4. Major surgery (major according to the investigator's assessment) performed within 10 weeks prior to randomisation or planned within 2 months after screening.
- 5. Any documented active or suspected malignancy or history of malignancy within 5 years prior to screening, except appropriately treated basal cell carcinoma of the skin or in situ carcinoma of uterine cervix.
- 6. Active skin disorders on the back where photosensitivity testing will be performed.
- 7. Subjects who must or wish to continue the intake of restricted medications (see section 4.2.2.1) or any drug considered likely to interfere with the safe conduct of the trial.
- 8. Subjects not expected to comply with the protocol requirements or not expected to complete the trial as scheduled (e.g. chronic alcohol or drug abuse or any other condition that, in the investigator's opinion, makes the subject an unreliable trial participant).
- 9. Currently enrolled in another investigational device or drug trial, or less than 30 days (or 5 half-lives (whichever longer)) since ending another investigational drug trial.
- 10. Women who are pregnant, nursing, or who plan to become pregnant while in the trial.
- 11. History of relevant allergy or hypersensitivity (including allergy to the trial medication or its excipients).
- 12. History of hypersensitivity to ciprofloxacin, any member of the quinolone class of antibacterials.
- 13. History of hypersensitivity to sunlight or artificial source of intense light, especially UV light.
- 14. Chronic or acute infections which are of relevance in the opinion of the Investigator.
- 15. Positive result for HIV, HBV, and hepatitis C (Hep C) at screening.
- 16. History of TB or positive finding in IGRA.
- 17. Unwillingness/inability to refrain from intake of alcoholic beverages from 48 hours prior to the trial medication administration and until Day 7 post trial medication administration.
- 18. Positive drug screening.
- 19. Blood donation of more than 500 mL within 30 days prior to administration of trial medication or intended donation during the trial.
- 20. Intention to perform excessive physical activities within 4 days prior to administration of trial medication or contact sport during the entire trial and unwilling to avoid vigorous exercise for 7 days post dosing.

01 Apr 2020

c27983101-03 Clinical Trial Protocol Page 36 of 79

Proprietary confidential information © 2020 Boehringer Ingelheim International GmbH or one or more of its affiliated companies

- 21. Inability to comply with dietary regimen of trial site.
- 22. Unwillingness to adhere to the rules of UV-light protection as described in section 4.2.2.
- 23. Received a live vaccination within 12 weeks prior to randomisation (visit 2), or any plan to receive a live vaccination during the conduct of this trial.
- 24. Subjects with known prolongation of the QT interval, risk factors for QT prolongation or torsade de pointes.

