1.4 BENEFIT - RISK ASSESSMENT

1.4.1 Benefits

Participation in this trial is without any (therapeutic) benefit for healthy subjects. Their participation in the trial, however, is of major importance to the development of BI 730357 and may help to generate future benefit for larger groups of patients with many disease indications.

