As with other immune-targeted therapies, impaired host defence is a theoretical target-related toxicity, potentially resulting in increased risk of infection and/or malignancy. Subjects with latent TB infection or TB disease, also subjects with HBV, HCV, HIV or any other clinically relevant bacterial or fungal infections will be excluded at screening.

Risk to subjects will also be minimized in this trial by implementing conservative eligibility criteria.

Homozygous, but not heterozygous RORC knockout mice have a high incidence of T cell lymphoma, thought to originate in the Thymus. While the translatability of the knockout phenotype to pharmacological RORγ antagonism and to humans is unknown, this raises the hypothetical concern for clinical T cell lymphoma risk. The exact cause of T cell lymphomas in RORC knockout mice is not fully understood, but changes in homeostasis in the thymus, such as thymocyte apoptosis and proliferation, are thought to play a role. AEs and SAEs consistent with malignancy, and specifically those representing lymphoma, will be carefully monitored and evaluated as well as monitoring of peripheral blood lymphocyte subsets will be integrated into this clinical trial.

An *in vivo* phototoxicity study in rats was conducted in pigmented rats. No cutaneous reactions indicative of phototoxic response were seen at 10 mg/kg/day, which corresponded to mean C_{max} and AUC_{0-24} values of 4,520 nM and 35,200 nM•h, respectively. No ophthalmic changes indicative of phototoxicity were seen up to 30 mg/kg/day, which corresponded to a mean C_{max} and AUC_{0-24} values of 13,500 nM and 107,000 nM•h, respectively.

Dose 400 mg BI 730357 planned to be tested in this study was administered once daily over a period of 4 weeks in the MRD study 1407-0002. The pharmacokinetic parameters observed in this study - AUC_{0-24} [nmol*h/L] 15,600 ($AUC_{\tau,ss}$ [nmol*h/L] 35,500) and C_{max} [nmol/L] 1320 ($C_{max,ss}$ [nmol/L] 2210) indicate that the plasma concentrations and exposures, which might be achieved in this study, are lower than those observed in *in vivo* phototoxicity study in rat where the phototoxic responses have been seen.

c27983101-03 Clinical Trial Protocol Page 23 of 79

Proprietary confidential information © 2020 Boehringer Ingelheim International GmbH or one or more of its affiliated companies

Ciprofloxacin

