Although rare, a potential for drug-induced liver injury (DILI) is under constant surveillance by Sponsors and regulators. Therefore, this trial requires timely detection, evaluation, and follow-up of laboratory alterations in selected liver laboratory parameters to ensure patients' safety (see also section 5.2.6.1.4).

Special precautions

The following safety measures will be applied in order to minimize the risk for healthy volunteers:

- Dose selection is based on a sound preclinical package, and safety, tolerability and PK data from MRD administration of BI 730357 up to 400 mg in healthy volunteers and preliminary safety data for up to 200 mg in patients with plaque psoriasis.
- Dose duration of 500 mg of ciprofloxacin bid over 5.5 days is a standard, well tolerated clinical dose
- Individual stopping rules as described in section 3.3.4.1 will be applied.
- UV-light protection measures as described in section 4.2.2.2 will be required until the end of study visit.
- The subjects will be kept in a Phase I unit during trial medication administration until completion of photosensitivity assessments 72 hours after last dose for safety evaluations. A careful clinical examinations will be performed during the trial, before the subjects are discharged from the clinic, and at the end of trial visit.
- Adverse events, body temperature, vital signs, ECGs and safety laboratories will be monitored at different time points during the trial. During the safety follow-up period all AEs, regardless of relatedness, will be collected up to 7 days after the last administration of trial medication.

Procedure-related risks

Blood sampling by venepuncture or through an indwelling venous catheter may be accompanied by mild bruising and also, in rare cases, by transient inflammation of the wall of the vein. In addition, in rare cases a nerve might be injured while inserting the venous catheter, potentially resulting in paraesthesia, reduced sensibility, and/or pain for an indefinite period.

The total volume of blood withdrawn per subject during this trial will not exceed the volume of a normal blood donation (500 mL). No health-related risk is expected from this blood withdrawal.

Boehringer Ingelheim

BI Trial No.: 1407-0037

Clinical Trial Protocol c27983101-03

Page 25 of 79 Proprietary confidential information © 2020 Boehringer Ingelheim International GmbH or one or more of its affiliated companies

01 Apr 2020

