5. ASSESSMENTS

5.1 ASSESSMENT OF PHOTOSENSITIVITY

Two Multiport Solar Simulator models 601 (will be used for irradiation (150 W or 300 W xenon arc lamp, dichroic mirror, and equipped with filters to produce UVA or UVA+B (290-400nm) outputs). This light source is equipped with 6 liquid light wave guides extending out of the case and an automated shutter device allowing for precise delivery of UV light doses per individual wave guide. Actual irradiation values delivered by the individual light guides will be recorded throughout the study using a PMA2100 Radiometer (equipped with a PMA2113 UVA sensor (physical irradiation in the range of 320 to 400 nm) and with a PMA2103 UVB sensor (biologically weighted, erythemal effective irradiation).

A series of unprotected naive skin test sites on the back will be irradiated with the following three different conditions, meant to simulate three different environmental sunlight exposure scenarios/conditions:

- 1. Condition 1: Full range solar UVB/UVA (290 to 400 nm, UBV content ~10%), simulating midday summer outdoor sun exposure (assessed in μ w/cm²).
- 2. Condition 2: UVA only (320 to 400 nm, UVB content <0.03%), simulating indoor exposure behind window glass with a secondary assessment of erythema and local skin reactions at 25 J cm⁻²(assessed in mw/cm²).

Subjects will be exposed to a series of 6 graded full range solar UVB/UVA exposures (Condition 1) and UVA only exposures (Condition 2), each 25% greater than the previous dose. Following irradiation, skin sites will be evaluated for erythema or skin darkening (for UVA-only exposure in the absence of additional, drug-induced phototoxicity).

The MED will be defined as the lowest dose that produced uniform redness (condition 1) or darkening (condition 2) (assessed in joules (J) for UVA and millijoules (mJ) for UVB/UVA).

An approximate MED_{preliminary} will be irradiated on day -3 and will be evaluated 10 min, 1 h and 24 h post irradiation. The initial MED_{preliminary} will be used to fine-tune the irradiation range for the determination of a precise MED_{baseline} on day -2. The MED_{baseline} irradiation will occur on day-2 and will be evaluated 10 min, 1 h and 24 h post irradiation.

Outpatient pre-treatment photosensitivity testing will occur prior to the dose administration on day 1 as follows:

Day -3

Irradiate Preliminary MEDs (Condition 1 and Condition 2) followed by MED assessments at 10 ± 2 minutes, 1 hour ± 5 minutes

Boehringer Ingelheim

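### Exclusion 5 does not automatically exclude volunteers with treated basal cell carcinoma or an older skin cancer from a trial built on deliberate UV irradiation, and the procedure risks in Protocol 1.4.2 omit that irradiation

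*Protocol*

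**What the plan says.** Exclusion 5 in Protocol 3.3.3 reads "Any documented active or suspected malignancy or history of malignancy within 5 years prior to screening", followed by "except appropriately treated basal cell carcinoma of the skin or in situ carcinoma of uterine cervix". Two other exclusions concern skin or light. Exclusion 6 is "Active skin disorders on the back where photosensitivity testing will be performed"; Exclusion 13 is "History of hypersensitivity to sunlight or artificial source of intense light, especially UV light".

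Section 5.1 describes the central procedure: "Subjects will be exposed to a series of 6 graded full range solar UVB/UVA exposures (Condition 1"; the sentence goes on to a matching UVA-only series for Condition 2. Each step is 25% above the one before. Irradiation is scheduled on Days -3, -2, -1 and 8.

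Under procedure-related risks, section 1.4.2 begins "Blood sampling by venepuncture or through an indwelling venous catheter may be accompanied by mild bruising" and goes on to vein inflammation, nerve injury and blood volume. The trial-procedures entry in the risk table repeats vein inflammation and nerve injury. Neither place mentions UV irradiation. The same section calls the eligibility criteria conservative, and section 1.4.3 concludes that healthy subjects face no undue safety risk. On benefit, section 1.4.1 states: "Participation in this trial is without any (therapeutic) benefit for healthy subjects".

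**The concern.** A malignancy criterion that excepts treated basal cell carcinoma and lapses after 5 years may serve in an ordinary drug trial. Here UV radiation is delivered on purpose, to skin types that burn, in volunteers with nothing to gain. A history of skin cancer is the part of a malignancy history most relevant to that procedure, and it is the part that Exclusion 5 treats most lightly. At stake is the protection of a small number of volunteers, and whether the stated benefit-risk conclusion covers the procedure that defines the trial.

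**Working it through.** The plan gives no figure to reproduce. The check sets the criteria, the irradiation schedule and the risk text side by side.

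**Who passes the criteria (Protocol 3.3.2 and 3.3.3)**

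- Exclusion 5: a treated basal cell carcinoma passes whatever its date, including within the 5 years. Any other skin cancer passes once its history is more than 5 years old.
- Exclusion 6: needs an active disorder, located on the back. A past, treated cancer does not meet it.
- Exclusion 13: needs hypersensitivity to light. Skin cancer history is not that.
- Inclusion 6: asks for a normal response at preliminary photo testing, so it applies only after the first irradiation and does not ask about cancer history.
- Inclusion 1, Exclusions 1 and 3: rest on the investigator's judgement of health and clinical relevance. They allow a refusal but set no rule.

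Section 6.2.1 lets only subjects who have met the general criteria go on to irradiation, so these criteria are the safeguard before the first UV exposure.

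**How much irradiation, and how much of it on treatment (Protocol 5.1)**

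- Graded sites per MED session: 6 steps × 2 conditions = 12.
- Days -2 and 8: 12 × 2 = 24 sites. If the Day -3 preliminary series also uses 6 steps per condition (an assumption; the text does not say), the total is 12 × 3 = 36.
- After dosing: the Day 8 session only, 12 sites. That is 12/24 = one half, or 12/36 = one third, of the graded sites.
- Half of each session (6 of 12) is Condition 2, UVA with UVB content below 0.03%.
- Condition 3 adds exposures on Days -1 and 8; the available text does not give their number.
- Dose range within a series: 1.25^5 = 3.05, so the top site receives about three times the lowest.

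**Who has an active drug on Day 8 (Protocol 3.2)**

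- BI 730357: 27 × 2 = 54. Placebo: 9 × 2 = 18. Ciprofloxacin: 12. Total 84.
- Irradiated after BI 730357, for which section 1.3 states phototoxicity potential, or after ciprofloxacin, a known photosensitiser: 54 + 12 = 66 of 84.

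**What 1.4.2 weighs**

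- Procedure risks: blood sampling and its complications.
- Phototoxicity: listed under the medicinal products, with sun protection and a ban on UV treatment as mitigation. Section 4.2.2.2 adds a ban on tanning beds and avoidance of direct sunlight.
- Malignancy: an effect of immune targeting, "potentially resulting in increased risk of infection and/or malignancy".
- The test irradiation: covered only by an opening sentence that refers to trial-procedure risks in general.

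The protocol thus restricts incidental UV exposure during the trial, but does not list the UV that it delivers itself.

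**The case against.** The strongest reply is that this is a clinical eligibility choice with no demonstrated harm. The sites are few, the doses are set around each subject's own MED, and section 5.7 describes an established method and trained staff. The investigator takes a complete medical history and may refuse anyone. Site counts and the 3.05-fold range describe the dose ladder, not a risk. All of that stands. That UV exposure matters to someone with a skin cancer history is general knowledge, not a figure from these documents.

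A reader might also infer four stronger things that the documents do not support.

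- That subjects are irradiated repeatedly while on a photosensitiser. Days -3, -2 and -1 precede dosing; only Day 8 follows it, and the 18 placebo subjects receive no photosensitiser.
- That the malignancy concern in 1.4.2 compounds the UV exposure. It is an immune-target concern, and nothing in the documents links it to UV or to recurrence of skin cancer.
- That the sponsor never assessed UV risk. The text shows an omission from the written procedure risks. Section 1.4.2 does discuss phototoxicity as a drug risk, and the consent pages, where irradiation may be described, are not available for this review.
- That such volunteers are entitled to enter. They are merely not excluded automatically.

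What remains is that discretion is not a rule, and that the one criterion addressing malignancy makes no allowance for this trial's own procedure.

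**Conclusion.** The point holds as a matter of subject protection and internal consistency. Exclusion 5 leaves skin cancer history to discretion in a trial where every subject has four irradiation days, and 1.4.2 names only blood sampling among procedure risks. That does not match the description of the criteria as conservative, and it leaves the conclusion in 1.4.3 without a stated basis for the irradiation.

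The size is modest. The documents give no count of affected volunteers; among healthy people aged 18 to 55 it is probably very small. They give no basis for quantifying the added risk. The endpoints, sample size, power and type I error do not depend on the criterion, and SAP 11.1 does not name Exclusion 5 among its examples of violations that could lead to exclusion of data. The conclusion rests on the text of the criteria and of 1.4.2, and on the general premise that skin cancer history is relevant to deliberate UV exposure. It does not depend on the assumption about the Day -3 series.

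**What to change.** Reconcile Exclusion 5 with the irradiation procedure. For this UV trial, remove the general-purpose basal cell carcinoma exception and the 5-year lapse as they apply to skin cancer history. The exact wording is for the sponsor's clinical team to set. In 1.4.2, list UV irradiation among the procedure-related risks and in the trial-procedures part of the risk table, with the revised criterion as its mitigation, so that 1.4.3 rests on an assessment that includes it.

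The cost is one eligibility sentence and one risk-table entry in an amendment, and a few volunteers who become ineligible. Treatment, assessments, sample size and power are unchanged.
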